### **3.5.9. Unanticipated Adverse Device Effect (UADE)**

For the US study subjects, per 21 CFR 812.3(s) “an unanticipated adverse device effect means any serious adverse effect on health or safety or any life-threatening problem or death caused by or associated with, a device, if that effect, problem, or death was not previously identified in nature, severity, or degree of incidence in the investigational plan or application, or any other unanticipated serious problem associated with a device that relates to the rights, safety, or welfare of subjects.”

If an adverse event is determined to meet the definition of a UADE, CVRx will immediately conduct an evaluation. If a UADE that represents an unreasonable risk for subject health, or a product performance failure becomes apparent, immediate action will be taken and the appropriate authorities will be notified. The investigator will be notified of the results of this evaluation. All UADE must be reported to CVRx within 10 working days after the site first learns of the event, and must be reported to all investigators, FDA and IRBs.

For other geographies, ISO 14155 defines an Unanticipated Serious Adverse Device Effect (USADE) as a serious adverse device effect which by its nature, incidence, severity or outcome has not been identified in the current version of the risk analysis report. Reporting of USADEs must follow country regulations.

### **3.6. Equipment, Instrumentation and Support**

CVRx will provide the following:

- Carotid Sinus Lead(s)
- Implant Tool
- Implant Adapters
- Implantable Pulse Generator
- Programmer System
- Magnet
- Accessory Kit
- CSL Repair Kit
- System Reference Guide
- All required Forms and Agreements
- Shipping materials to return investigational devices and trial data
- Support for implants and follow-ups as available
- Protocol, implantation and device operation training
- Subject identification cards
- Electronic Data Capture (eDC) database and support
- Blood corelab materials

The Participating Institution will provide the following:

- Expertise in the care and management of subjects with heart failure
- All facilities, equipment and expertise required for CSL and IPG implantation
- Capabilities and facilities to collect all required data
- Appropriately trained personnel to handle and ship blood

### 3.7. Investigator Certification

All investigators participating in this trial are expected to fully execute the CVRx Investigator Agreement for the trial. Investigational devices will not be provided to any investigator prior to the receipt of the signed agreement.

### 3.8. Surgeon Training

Surgeon Investigators must be trained in order to implant the BAROSTIM NEO System. The training process will require:

- Training on implant procedure, anesthesia, and BAROSTIM NEO System operation.
- A minimum of two proctored implants of the BAROSTIM NEO System with a CVRx-certified proctor (inclusive of any prior BAROSTIM NEO System implant experience).

### 3.9. Device Accountability, Handling and Storage

This trial will utilize CVRx Implantable Pulse Generators (IPGs) and Carotid Sinus Leads (CSLs). These devices will be labeled as Investigational Devices and will require special handling and storage controls. All IPGs, CSLs, Programmers, CSL Repair Kits, and accessory kits delivered to the institution will be recorded by serial number on a Device Accountability Log. In addition, the date received, date used (or attempted), subject ID, date returned to CVRx, date destroyed, and any comments will be recorded in the Device Accountability Log.

All IPGs and leads utilized in the trial will be recorded in the trial database. Upon conclusion of the trial all unused and any explanted IPGs and CSLs will be returned to CVRx in the device shipment materials provided.

### 3.10. Termination of Therapy

Careful consideration should be given to whether the device is turned off immediately or if therapy is gradually reduced over a period of time. It is important that each subject be adequately monitored during this transition period. It is recommended to wait at least 30 days following termination of therapy prior to explanting the device to allow for an assessment of the subject status. If the decision is made by the subject or clinician to withdraw or partially withdraw from the trial, the Baroreflex Activation Therapy can continue outside the study. The investigator should discuss the options for following routine care of the system, turning off the device or explanting the IPG including the potential risks of each. It is recommended that the Carotid Sinus Leads should not be explanted, and the leads should be left implanted with the leads capped.

If any portion of the system is removed, the subject should be followed for at least 30 days post-explant for any possible adverse events. If the subject has any ongoing system- or procedure-related adverse events at this time, they should continue to be followed until resolution of these events or the subject's condition is stable. The final status of the IPG should be documented in the subject's medical records as well as in the trial database. A trial termination form should be completed.

### 3.11. Final Trial Visit

If the subject has any ongoing system- or procedure-related adverse events at the time of the final trial visit, these events will be listed as unresolved. If the subject decides not to continue to receive therapy, please refer to Section 3.10 Termination of Therapy. A trial termination form should be completed indicating the “subject completed trial per protocol” and the date of the final trial visit.

### 3.12. Withdrawal of a Subject

A subject may be withdrawn or partially withdrawn from the trial at any time by the investigator for a variety of reasons including, but not limited to, the subject not following trial-related directions, or a serious reaction develops or implantation of the BAROSTIM NEO System in countries where the device is market approved. A subject may also choose to voluntarily withdraw consent for the trial or from receiving further trial treatment at any time. The subject’s eligibility for continuing medical care will not be affected by his/her withdrawal from the trial.

The investigator should discuss the decision with the subject and clearly document the reason, date of discussion and who participated in the discussion along with the items discussed in the subject’s medical record. Note the non-US PIs will make every effort to encourage the subjects to stay in the trial to their assigned randomization before opting out to a BAROSTIM NEO implant.

Should a subject express the desire to withdraw from the study, the subject should be made aware of the option to partially withdraw from the study. This may be done through a consent form for subjects who wish to discontinue active follow-up in the trial, but not fully withdraw. The objective of the partial withdrawal is to allow site personnel continued access to subject medical records in order to collect information for the morbidity and mortality endpoint. Please refer to Section 3.4.5 Partial Withdrawal

For subjects who progress in their heart failure status to receive either a cardiac assist device or a heart transplant, see Section 3.15.

### 3.13. Lost to Follow-Up

It is strongly recommended that multiple telephone numbers should be obtained from the subject to ensure the ability to contact him or her for the required follow-up visits. These phone numbers should include all home/mobile numbers, work numbers (if applicable) and their primary physician numbers. A phone number of a relative or friend should also be requested.

If a subject cannot be reached for a follow-up visit, the site will complete a protocol Deviation Case Report Form. The efforts undertaken to contact the subject, family members, or other alternate contacts should be noted in the subject’s records. These efforts should include at least 2 attempts of telephone contact on separate dates, and at least two weeks of non-response after a certified letter sent to the last known address.

If two consecutive protocol-required visits meet the above criteria, a subject is considered lost to follow-up. As the subject has not withdrawn consent, the subject may remain active in the database to collect any available data. At the end of the study they will be considered permanently lost-to-follow.

### **3.14. Discontinuation of Therapy**

Circumstances may arise during the trial that require the device to be temporarily or permanently turned off for a subject. This may include an adverse event, an intercurrent illness or other medical condition where continued therapy would not be in the best interest of the subject, or subject's wish.

If the device is turned off temporarily, the reason should be clearly noted in the subject's medical records and a Programming CRF should be completed to document the date.

### **3.15. Cardiac Assist Device or Heart Transplant**

Subjects in either treatment arm who progress in their heart failure status to receive either a cardiac assist device or a heart transplant must be withdrawn from the study. For subjects with an active BAROSTIM NEO device in geographies where the device is not approved, the device must be permanently turned off prior to the cardiac assist device or heart transplant procedure (see Section 3.10). The investigator should discuss the options for either leaving the IPG in place or for explanting the IPG including the potential risks of each. It is recommended that the Carotid Sinus Leads should not be explanted, and the leads should be left implanted with the leads capped. These device subjects must be followed for 30 days after the termination of device therapy or after the explanting of any of the BAROSTIM NEO System.

## **4. ENDPOINTS, STATISTICAL METHODS AND DATA ANALYSIS**

### **4.1. General Principles**

The primary analysis for all baseline characteristics and trial outcomes will include all randomized subjects, unless specified otherwise. Standard summary statistics will be calculated for all trial variables. For continuous variables, statistics will include means, standard deviations, medians and ranges. Categorical variables will be summarized in frequency distributions.

For effectiveness outcomes, primary analyses will be conducted on an intent-to-treat (ITT) basis, for which subjects are analyzed according to their randomized assignment irrespective of the treatment received. The safety analysis will include all subjects where an implant has been attempted.

Statistical analyses will be conducted in SAS version 9.3 or above (SAS Institute, Cary, N.C.) or another validated statistical software.

Details on the analyses defined below, as well as supportive and ancillary analyses, will be provided in a Statistical Analysis Plan (SAP). Any deviation from the protocol or the SAP will be discussed and based on sound statistical rationale. Endpoints and analyses defined in a Statistical Analysis Plan supersede the definitions in this protocol.

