## 2. PURPOSE

The purpose of this clinical trial is to develop valid scientific evidence for safety and effectiveness of Baroreflex Activation Therapy® with the BAROSTIM NEO System in subjects with heart failure, defined as New York Heart Association (NYHA) functional Class III, left ventricular ejection fraction (LVEF)  $\leq$  35% and NT-proBNP < 1600 pg/ml despite being treated with the appropriate heart failure guideline directed therapy, excluding subjects eligible for or actively receiving Cardiac Resynchronization Therapy (CRT).

The total trial duration is anticipated to be approximately 5 years; however, the duration of an individual subject enrollment will depend on when he or she entered the trial.

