## 3. PROTOCOL

### 3.1. Trial Summary

The BAROSTIM NEO - Baroreflex Activation Therapy for Heart Failure is a prospective, randomized trial in subjects with reduced ejection fraction heart failure. Subjects will be randomized in a 1:1 ratio to receive Barostim Activation Therapy with an implanted BAROSTIM NEO System in addition to medical management or to receive medical management alone (no device implant). The trial will be conducted at up to 120 investigational centers in the U.S. and up to 20 investigational centers outside the U.S. These centers will enroll up to 1200 subjects to randomize approximately 480 subjects who meet the entry criteria.

A single center will not be permitted to randomize more than 15% of the total number of randomized subjects. A subject will be considered enrolled when he or she has provided written consent.

Post-consent screening measurements will be obtained only after the subject has completed a medication optimization and 4-week medication stabilization period. For all subjects, the heart failure medication regimen must remain stable during the 4-week medication stabilization period, except for minor adjustments (see inclusion criterion #5 in section 3.3.1). Subjects will be randomized when they have met all enrollment criteria and after all baseline measurements have been obtained.

Prior to randomization, site personnel will be required to provide an anticipated implant date. For subjects randomized to the Medical Management Arm, this date will be used for the timing of all other trial visits. For subjects randomized to the Device Arm, trial visits will be based on the actual date of device implant.

Device subjects will have the device activated prior to being discharged from the hospital, and should remain at the hospital for at least 2 hours post-programming for observation prior to being discharged. At the physician's discretion subjects may remain overnight for observation to evaluate programming.

For all subjects, trial visits will occur at 0.5, 1, 1.5, 2, 3, 6, 9 and 12 months post-implant (post anticipated implant for medical management). Visits will occur quarterly from 15 to 24 months and semi-annually thereafter.

Subjects are followed in an identical manner regardless of trial arm.

Figure 7 provides a schematic of the overall trial design.

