#### 3.5.2. Adverse Event Reporting

Once a subject is enrolled (enrolled is defined as the date the subject provided written consent), all adverse events must be reported until the subject is withdrawn or is terminated from the trial. All reported events regardless of geography will be reported in study reports (e.g. annual reports).

In addition, all adverse events that occur in OUS subjects will also be reported according to ISO 14155:2011, while recognizing and following the requirements including reporting timelines specified in other specific laws, regulations, directives, standards and/or guidelines as appropriate.

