#### **6.4. Procedure Related Complications - Implant and 30 days Post-implant**

Incidence of procedure related complications occurring between implant and 30 days post-implant will be analyzed descriptively with frequency counts and percentages for the safety population. The numerator will include the number of subjects with at least one procedure related complication occurring between implant and 30 days post-implant. The denominator will include subjects who have had an implant, or an implant attempted.

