#### **6.5. System Related Complications – 30 day to 6 months Post-implant**

Incidence of system related complications occurring between 30 days and 6 months post-implant will be analyzed descriptively with frequency counts and percentages for the safety population. The numerator will include the number of subjects with at least one system related complication occurring between 30 days and 6 months post-implant. The denominator will include subjects who have had an implant, or an implant attempted.

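### Apart from mortality and the heart failure events in the M&M endpoint, neither the protocol nor the SAP supplement plans a between-arm comparison of adverse events, because the stated safety set is attempted implants only

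*Protocol*

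**What the plan says.** The purpose of the trial (Protocol 2) is to develop "valid scientific evidence for safety and effectiveness". Protocol 3.1 gives the design: "Subjects will be randomized in a 1:1 ratio", to device plus medical management or to medical management alone.

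Protocol 4.1 sets a default population: "The primary analysis for all baseline characteristics and trial outcomes will include all randomized subjects, unless specified otherwise". It then specifies otherwise for safety: "The safety analysis will include all subjects where an implant has been attempted".

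The SAP supplement has two complication analyses, both under the ancillary endpoints, for which it sets no formal hypotheses:

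- SAP 6.4, procedure-related complications from implant to 30 days: "The denominator will include subjects who have had an implant, or an implant attempted".
- SAP 6.5, on the same denominator: "Incidence of system related complications occurring between 30 days and 6 months post-implant will be analyzed descriptively".

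Collection of adverse events is not limited by arm. Protocol 3.1 says: "Subjects are followed in an identical manner regardless of trial arm". Under Protocol 3.5.2, from written consent onward, "all adverse events must be reported until the subject is withdrawn or is terminated from the trial". Table 5 requires adverse events at every follow-up visit; only the implant and activation contacts are device-only.

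Relatedness is assessed by the investigator (Protocol 3.5.3). The Adverse Events Committee, which may reclassify events, is not blinded to arm (Protocol 5.2).

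**The concern.** Some of the device risks named in Protocol 6.2 (stroke, arrhythmia, hypotension, systemic embolization) can be expected in a heart failure population without a device. Stroke, acute myocardial infarction and systemic thromboembolism are also MANCE components (Protocol 3.5.8). For such events a rate among implanted subjects cannot separate device harm from background. Attribution has to be made event by event, by people who mostly know the arm.

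The randomized control arm could answer the question without attribution. If it is not used, a device-arm excess of non-fatal, non-heart-failure events could go unseen, or background events could be charged to the device. Safety is half of the stated purpose, so both errors matter.

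**Working it through.** The documents attach no sample size, power or precision to the safety analysis, so there is no planned figure to reproduce. The check sets the passages side by side and then sizes the comparison that the data would allow.

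**1. Who is in the stated safety set.** Subjects with an attempted implant: in practice the device arm. SAP 1 reports four subjects in the NT-proBNP subgroup who were randomized to treatment and never implanted; they fall outside the set unless an implant was attempted. Read literally, the wording also admits a control subject who receives an out-of-protocol BAROSTIM (SAP Table 3, item 5). Control subjects as randomized are not in it.

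**2. What SAP 6.4 and 6.5 count.** Three limits apply together:
- Only events judged procedure- or system-related. Protocol 3.5.3 has an unknown category, and neither SAP section says how it is counted.
- Only complications, meaning death, permanent injury or an invasive intervention to prevent either (Protocol 3.5.6). An admission for arrhythmia or hypotension treated medically, without permanent injury, is an observation and drops out.
- Only the first 6 months after implant, whereas Protocol 4.3.3 expects a mean of 2.3 years of follow-up for the M&M endpoint.

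**3. What is compared between arms.**

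| Event | Between-arm analysis in the supplied documents |
|---|---|
| CV death, HF hospitalization or ER visit, assist device, transplant | Yes: Protocol 4.3, SAP 3.1; components in SAP 5.4 |
| All-cause death | Yes: SAP 5.10, hazard ratio |
| The M&M endpoint in all randomized subjects, from randomization | Yes: SAP 4.3 |
| Non-fatal stroke, MI, arrhythmia, hypotension, embolism | None found |
| All adverse events; all serious adverse events | None found |
| MANCE, other than the components above | None found; SAP Table 1 places MANCE in the expedited submission and leaves it blank in the M&M column |

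**4. What a by-arm comparison could show.** Inputs: 323 randomized in the subgroup and 319 in the M&M analysis (SAP 1), so 323/2 = 161.5 and 319/2 = 159.5, or about 160 per arm. For all 467 randomized (SAP 7), 467/2 is about 233 per arm. Equal arms are assumed. The documents give no background adverse event rates, so the incidences p below are assumptions.

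Half-width of the 95% CI for a difference, with the same p in both arms: 1.96 × √(2p(1−p)/n).

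For p = 0.03 and n = 160: 1.96 × √(0.0582/160) = 1.96 × 0.01907 = 0.037.

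| Assumed incidence | n = 160 per arm | n = 233 per arm |
|---|---|---|
| 3% | 3.7 points | 3.1 points |
| 5% | 4.8 points | 4.0 points |
| 10% | 6.6 points | 5.4 points |
| 15% | 7.8 points | 6.5 points |

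In power terms (two-sided 5%, 80% power), 161 per arm would detect an excess of 9.2 points over an assumed control rate of 5%, and 11.4 points over 10%. With 233 per arm the figures are 7.3 and 9.2 points. The comparison is useful for common events and weak for rare ones.

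**The case against.** The best defence has four parts.

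**Controls already serve as comparators for the gravest harms.** A reader might infer from the safety sentence that the randomized controls play no part in judging whether the device causes excess events. The documents do not support that. The analyses in the first three rows of the comparison table are framed as benefit, but a device-arm excess of death or heart failure events would appear in them. This part stands in full, and worsening heart failure that leads to hospitalization or an ER visit does not belong among the uncompared harms.

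**Absence cannot be proved from these documents.** The supplied SAP supplements a main SAP that was not provided, and Protocol 4.1 leaves supportive and ancillary analyses to a SAP that overrides the protocol. A reader might infer that no such comparison exists anywhere; the claim can be made only for the protocol and the supplement. This stands as a limit on the point.

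**The sentence says whom the safety analysis includes and does not forbid other tables.** Protocol 4.1 promises summary statistics for all trial variables, and 3.5.2 says reported events will appear in study reports. That is correct, but neither commits to a comparison by arm, and the all-randomized default gives way where a population is specified otherwise, as it is for safety. This part stands only partly.

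**Adjudication is not wholly unblinded.** MANCE goes to the Adverse Events Committee and the Clinical Events Committee (Protocol 3.5.8), and the latter is blinded (Protocol 5.3). This stands: unblinded attribution concerns investigators and the Adverse Events Committee.

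It could also be inferred that the attempted-implant set is itself wrong. It is not: unimplanted controls cannot have procedure- or system-related complications.

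**Conclusion.** The point holds in a limited form. In the supplied documents, non-fatal events outside the heart failure endpoint have no planned between-arm comparison, although adverse events are collected in both arms at the same follow-up visits. The gap follows from a stated analysis set and does not extend to mortality or to the heart failure events of the M&M endpoint.

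Nothing in the plan is numerically contradicted. The half-widths show what could be estimated; they do not measure a bias. They rest on assumed incidences, equal arms and simple proportions without allowance for exposure. At 3% the half-width (3.7 points with 160 per arm) exceeds the rate itself, so a moderate excess of a rare event such as stroke could still be missed after the change. The conclusion is conditional on the main SAP (360050-001) not already containing the comparison.

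**What to change.** 1. Keep the attempted-implant set for procedure- and system-related complications (SAP 6.4 and 6.5).
2. Amend Protocol 4.1, and add a SAP section, so that all adverse events, all serious adverse events and the MANCE components that can occur in either arm are also summarized regardless of relatedness. Use all randomized subjects by assigned arm, counted from randomization, with exposure-adjusted rates, between-arm differences and 95% CIs. Starting at randomization matches SAP 4.3 and retains the never-implanted device subjects, who have no actual implant date.
3. Report the device-specific MANCE components separately in the attempted-implant set: infection requiring explant, restorative procedures for placement, and cranial nerve damage from the lead or therapy. An unsplit MANCE difference would count against the device events that controls cannot have.
4. Analyse control subjects who receive an out-of-protocol BAROSTIM as randomized, with censoring at implant as a sensitivity analysis.
5. If the main SAP already contains these tables, add a cross-reference instead.

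The cost is wording in two documents and a few descriptive tables from data already collected. Two limits should be stated beside the tables: open-label reporting may differ by arm, and precision is low for rare events.
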